2.3 Framework

The framework for the statistical analysis will test for superiority: the primary objective is to determine whether the FHT QI program increases appropriate follow-up in patients identified as at risk of an undiagnosed cancer.

2.4 Interim analyses and stopping guidelines

No formal interim analyses are planned for this trial. As the data used in this study is EMR data extracted from general practice, no formal data monitoring was required and there are no stopping guidelines in place.

2.5 Data management and workflow

General practice and practice staff characteristics will be collected via survey before randomisation.

Patient characteristics, baseline measures and outcome data will be measured using patient data extracted from general practice EMRs and stored in the Patron database. Patient and practice data will be extracted from each practice using the GHRANITE tool at each data collection period (4th October 2021 (baseline), 4th April 2022 (6 months), 4th July 2022 (9 months) and 30th September 2022 (12 months). The extracted data will be processed and curated by Patron data team members and stored within the Patron enclave using a separate database for each data collection period. This process takes approximately two weeks.

The FHT QI module installed within practices as part of the FHT intervention interacts with the practice EMR system, running the FHT algorithms over patient data to identify patients at risk of an unidentified cancer that may benefit from further follow up. The criteria used to identify the eligible patients at risk of an unidentified cancer who attend general practice and the creation of the recommendations for guideline concordant care to consider (flags) are outlined in the Future Health Today business requirements document which was used to develop the FHT algorithms embedded in the technology platform. Within participating general practices individual patient level recommendations can be viewed. However, only aggregate level data are extracted by Future Health Today platform and available to the research team. As a result, these data are not linked with Patron database used for the trial statistical analysis. Therefore, part of this curation process is the replication of the eligible patients and flags generated by FHT algorithms in the practices, patient outcomes and baseline measures, using identical algorithms to those embedded within, and executed by, FHT platform within the Patron dataset. These algorithms were independently validated by the biostatistician using baseline data. A limitation of this approach is that we will only be able to derive the action taken by clinicians if they were recorded in an extractable field in the EMR that is included in the Patron dataset, such as pathology results, medication prescriptions written, and observations.

All data within the Patron enclave is deidentified with patient and practice identifiers replaced by a unique hashed code prior to the data leaving the general practice. Data managers and analysts can access the databases for the project and utilise Structured Query Language (SQL) queries to create Comma Separated Values (CSV) files containing the data required for the trial analysis. Files downloaded from the Patron databases will be saved within a secure virtual machine accessible only by the study biostatisticians, health economists and the data manager. The virtual machine requires multifactor authentication to access. Within the secure virtual environment, the data manager or statisticians will then import the CSV data files into Stata Statistical Software⁹ for data processing and statistical analysis. Data will be checked for errors, resolving them where possible. Labelling, recoding,

and the creation of composite variables will be carried out, where required. Data from each data collection period will be collated using the unique patient identifier.

The statistical analysis for the cancer-risk study will be conducted by a PhD Candidate and the study biostatistician, with oversight from the senior biostatistician. The senior biostatistician will review the statistical analyses and will explicitly check the Stata programming code for the statistical analysis, reporting and interpretation of the results. Health economists will be responsible for the analyses related to the health economics component of the trial. The files for the final analysis will be stored within the secure virtual environment, as well as all subsequent outputs including (but not limited to) Stata .do, .dta, .log and .gph files.

The data analysts conducting the analysis and study investigators not involved in practice support and engagement will remain masked to the allocation of practices. Masking will be maintained as general practices are de-identified by the GRHANITE data extraction tool and assigns a unique code to the general practice records and patient codes. The study arm codes made available to the biostatistician conducting the analysis will be uninformative. The results for the primary outcome for the cancer-risk study will initially be presented to the FHT investigators using the uninformative study code to maintain masking and will be revealed after the results have been interpreted.

2.6 Timing of final analysis and outcome assessments

Statistical analyses for the cancer-risk study will commence in September 2023 after the Statistical Analysis Plan has been uploaded to the Australian and New Zealand Clinical Trials Registry.

Primary and secondary outcomes will be assessed at the trial end date, 30th September 2022, approximately 12-months after the trial start date, 4th October 2021. Subsequent references to the trial period refer to this 12-month period. The outcomes will reflect the status of each patient at the trial end date, based on their recorded observations, investigations and/or pathology test results in the EMR.

Baseline measures of the outcome and patient characteristics will be assessed at the trial start date (4th October 2021). The baseline measures for eligible patients will be based on the history of pathology test results in the EMR, in the preceding 6 months from the 4th of October 2021 for raised PSA, and the preceding 12-months for markers of anaemia and raised platelets.

3 Statistical principles

3.1 Level of statistical significance and confidence intervals

Estimates of the intervention effect will be reported with 95% confidence intervals and two sided-p-values.

3.2 Adjustment for multiple tests

No adjustments will be made for multiplicity. Separate sample sizes were determined for the respective primary outcomes for the cancer-risk and CKD studies and different samples will be drawn from the respective populations for the two studies. The total number of practices recruited in the trial were based on the sample size required for the CKD arm of the trial.

3.3 Adherence and protocol deviations

Protocol deviations include technical issues resulting in FHT being inaccessible for periods throughout the trial and preventing the extraction of data to the Patron system. Technical issues with FHT, practice

computers/servers (preventing upload of data or function of FHT) or other technical issues that prevent staff from accessing FHT could negatively impact on the ability of GPs to participate in the quality improvement program and to receive recommendations to facilitate delivery of guideline concordant care to patients within their cohort and may attenuate the effect of the intervention. Practices allocated to the control arm will only have access to the QI CKD program.

4 Trial population and Statistical Analyses

4.1 Primary outcome

The **primary outcome** is the proportion of eligible patients identified as at risk of undiagnosed prostate, oesophageal, gastric, colorectal, endometrial, lung or ovarian cancer that have been assessed and investigated according to NICE², Cancer Council Victoria⁴, Victorian Government Department of Health and Human Services⁸, Prostate Cancer Foundation of Australia guidelines⁵, within the 12-month trial period. The absence of any relevant recorded investigation, prescription, observation, or diagnosis during the trial period will be considered equivalent to the patient not being assessed or investigated.

The primary outcome will include any relevant investigation, dependent on whether patients were identified as at risk of cancer for iron deficiency anaemia, raised platelets or raised PSA. The relevant investigation must occur between being identified as at risk of an undiagnosed cancer (either at baseline or within the following 6 months), and the trial end date (30th Sept 2022).

For each patient identified as at risk of cancer with one or more markers of anaemia, a relevant investigation includes a repeat full blood count, iron studies, coeliac disease serology, FOBT, transvaginal ultrasound, referral to gastroenterologist, assessment of upper or lower GI symptoms and/or haematuria, prescription of an oral supplement and/or record of an iron infusion.

For each patient identified as at risk of cancer with a raised platelet count, a relevant investigation includes a repeat platelet count, chest x-ray, chest CT, FOBT, CA-125, transvaginal ultrasound, assessment for symptoms for lung, colorectal, gastro-oesophageal, ovarian or endometrial cancer, referral to a gastroenterologist, respiratory physician, or gynaecologist.

For each patient identified at risk of cancer with a raised PSA, a relevant investigation includes a repeat PSA test, free to total PSA percentage and/or referral to a urologist.

For any patient identified as at risk of cancer with more than one altered test result (e.g., anaemia and raised platelets), we will consider a relevant investigation from either marker as the equivalent of being assessed and investigated according to guidelines. In usual care, it is expected that the GP would prioritise care or use a sequential manner in responding to multiple possible investigations.

EMR data will be used to determine if an investigation has occurred. The reason for encounter, reason for prescription and diagnosis fields will be reviewed for relevant symptoms. Documents in, documents out and the diagnosis fields will be reviewed for specialist referrals. For other investigations, the requests, results, investigations, prescription and prescription reason fields will be explored.

4.2 Secondary outcomes

Secondary outcomes will include the individual indicators for guideline concordant care, including pathology test results, investigations, prescriptions, referrals, diagnosis, time to investigation and

number of encounters of patients that attended included general practices during the 12-month period.

- (1) The proportion of eligible patients identified in the closed and open cohorts with markers of anaemia, that have subsequently been followed-up according to guidelines^{2,6} within the 12-month trial period. Relevant investigations include a repeat full blood count, iron studies, coeliac disease serology, FOBT, transvaginal ultrasound, referral to gastroenterologist and/or assessment of upper or lower GI symptoms and/or haematuria. The absence of any of recorded investigation during the trial period will be considered equivalent to not being investigated.
- (2) The proportion of eligible patients identified in the closed and open cohorts with markers of anaemia, that have subsequently been prescribed an oral supplement and/or have a record of an iron infusion in the 12-month trial period. The absence of any recorded prescription for an oral supplement or iron infusion will be considered equivalent of the patient not being prescribed an oral supplement or iron infusion.
- (3) The proportion of eligible patients identified in the closed and open cohorts with raised platelet count, that have subsequently been followed-up according to Victorian Department of Health⁴, NICE² and Cancer Council⁴ within the 12-month trial period. Relevant investigations include a repeat platelet count, chest x-ray, chest CT, FOBT, CA-125, transvaginal ultrasound, assessment for symptoms for lung, colorectal, gastro-oesophageal, ovarian or endometrial cancer and/or referral to a gastroenterologist, respiratory physician, or gynaecologist. The absence of any of relevant recorded investigation during the trial period will be considered equivalent to not being investigated.
- (4) Proportion of eligible patients whose sex at birth is coded as male in the EMR in the closed and open cohort with one raised PSA that have been followed up according to Cancer Council Australia guidelines⁴ within the 12-month trial period. Relevant investigations include a repeat PSA test, free to total PSA percentage and/or referral to a urologist^{5,8}. The absence of any of relevant recorded investigation during the trial period will be considered equivalent to not being investigated.
- (5) Proportion of eligible patients in the closed and open cohorts that have a new recorded diagnosis of prostate, oesophageal, gastric, colorectal, endometrial, lung or ovarian cancer recorded in the general practice EMR within the 12-month trial period. The absence of any of recorded diagnosis during the trial period will be considered equivalent of no diagnosis being made.
- (6) The rate of general practice encounters per eligible patient over the 12-month trial period. This will be calculated using total number of general practice visits over the trial period of all eligible patients identified as at risk of an undiagnosed cancer in the closed cohort divided by the total time they were observed in the trial. For each patient, time will be calculated from the date the trial commenced (4th Oct 2021) to the end of the trial (30th September 2022). If the patient enters in the open cohort, the time observed will be calculated from the date they the trial to the end of the trial (30th September 2022). For patients/practices that discontinue during the trial period, time observed will be calculated from they entered the (namely, the 4th October 2021 for the closed cohort or date they first report of an abnormal test result for the open cohort) to the date the patient(s) discontinued/withdrew from the trial.

(7) Time to investigation for patients with abnormal pathology results identified as at risk of an undiagnosed cancer in the open cohort. This includes any investigation, treatment, review of symptoms or referrals as described in the primary outcome. Time to investigation will be defined as the number of days between the initial altered test result date and the first investigation (retesting, investigations, treatments, referrals and review of symptoms). Outcomes will be assessed at 12 months from baseline and patient records without follow-up action by this time will be censored.

Health economics outcomes are:

- (8) The cost of the installation for the software program for QI, training, QI support and education. This will be calculated at the general practice level, using cost data collected by Health and Biomedical Informatics Centre (HABIC R²) who developed and provided technical support for the FHT software and the FHT investigators and research team who liaised with practices and facilitated the education sessions.
- (9) Cost of primary care service utilisation per patient per year. These will be calculated based on Medicare items, Provider Charge, Schedule Fee, Patient Out of Pocket in the Medicare Benefits Schedule (MBS) data linked to patients in the Patron for the FHT evaluation.

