4.6.2 Secondary outcomes

Statistical methods described for the primary outcome will be used for the **binary secondary outcomes 1, 2, and 6.** For each outcome, an additional covariate will be fitted in the regression model. For outcome 1, we will adjust for whether a recommendation would have been made to consider initiating ACEIs or ARBs for the patient (yes/no). Similarly for outcome 2, we will adjust for whether the recommendation would have been received to consider initiating statins (yes/no). For outcome 6, we will include uACR at baseline as a covariate.

For the analysis of continuous secondary **outcomes 3, 4, 5 and 8**, a mixed effects linear model with study arm, baseline measure of the outcome (where appropriate), randomisation stratification factors (GP FTE and IRSD terciles) will be fitted as fixed effects and general practice as a random effect. The estimated intervention effects will be reported as the difference in means between the intervention and active control arms with 95% confidence intervals and p-values.

Outcomes with a skewed distribution may be log-transformed, in which case, the estimated intervention effect will be reported as a ratio of the geometric means between study arms, with their respective 95% confidence interval and p-value.

Secondary outcome 7 will be analysed using the proportional odds logistic regression model with randomisation stratification factors (GP FTE and IRSD terciles) and baseline CVD risk group included as fixed effects. Generalised Estimating Equations with an exchangeable correlation structure and robust standard errors will be used to allow for correlation of outcomes within general practice. An alternative model will be considered if the assumption of proportional odds is not met.¹¹

The estimated intervention effect will be reported as a cumulative odds ratio with their respective 95% confidence interval and p-value.

Secondary outcome 9 will utilise a Poisson mixed effects model (or a Negative Binomial mixed effects model if overdispersion is detected), with fixed effects for study arm and the randomisation stratification factors (GP FTE and IRSD terciles), and random effect for general practice. The estimated intervention effect will be reported as differences in rate between the intervention and control arms and rate ratios with 95% confidence intervals and p-values.

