2.2 Patient eligibility and exclusion criteria

Eligible patients will be identified as at risk of cancer by applying at least one or more of the following criteria:

At baseline – 4th October (**closed cohort**):

- Patients aged 50 to 80 years (inclusive) without a recorded GI, unspecified or metastatic cancer in the last 5 years who have one marker of anaemia (defined as Hb <130g/L in men and <115g/L in women or MCV <80fl or MCH <27pg or ferritin<30µg/L) in the past 6 months or two consecutive markers of anaemia in the past 12 months.
- 2. Males aged 40 to 80 years (inclusive) without a recorded diagnosis of lung, colorectal, gastrooesophageal or unspecific cancer in the previous 5 years or females aged 40 to 80 years old without a diagnosis of lung, colorectal, gastro-oesophageal, ovarian, endometrial or unspecific cancer in the previous 5 years who have one elevated plated count (defined as platelet count > 400×10^{9} /L) in the past 6 months or two consecutive elevated platelets counts in the past 12 months.
- 3. Males, aged 40-80, without a recorded diagnosis of prostate cancer with a raised PSA (defined as male aged 40-49 PSA > 2.0 ng/ml; male aged 50+ PSA> 3.0 ng/ml) in the past 6 months.

4th Oct 2021 - 4th April 2022 (**open cohort**):

- 4. Eligible patients not captured at baseline, with one or more markers of anaemia between October 4, 2021, and April 4, 2022.
- 5. Eligible patients not captured at baseline with an elevated platelet count between October 4, 2021, and April 4, 2022.
- 6. Eligible patients not captured at baseline with an elevated PSA between October 4, 2021, and April 4, 2022.

The terms closed and open cohort refer to when the patients were identified as at risk of cancer: at baseline, or during the first 6-months of the trial, respectively. Subsequent references to the closed and open cohorts refer to these eligibility criteria and the timeframes used to identify these patients.

Exclusions:

- 1. Patients that are recorded as no longer active in the general practice or deceased in the EMR.
- 2. Patients that are pregnant at baseline.

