4.3 Baseline practice, practice staff and patient characteristics

Baseline practice and practice staff characteristics include:

- State (Victoria, Tasmania)
- IRSD terciles based on the Index of Relative Socio-Economic Disadvantage (IRSD) ¹⁰ using the practice postcode. The first tercile represents relatively disadvantaged sociodemographic geographic areas compared to geographic areas with higher ranks (Tercile 3).
- Practice participation in a formalized QI program in the past 6 months (yes, no)
- Practice size based on the GP full-time equivalent (FTE) of 4 or less FTE or greater than 4 FTE as reported by the practice. FTE will be defined as the total number of full-time GPs plus the total number of part time GPs multiplied by 0.5FTE.
- GPs sex (male, female)
- GPs age group (<35 years; 35 to 50 years; >50 years)
- Number of FTE registered nurses. FTE will be defined as the total number of full-time nurses plus the total number of part time nurses multiplied by 0.5FTE.
- Registered nurses' sex (male, female)
- Registered nurses age group (<35 years; 35 to 50 years; >50 years)
- Number of FTE practice managers and administrative staff. FTE will be defined as the total number of full-time practice managers/administrative staff plus the total number of part time practice managers/administrative staff multiplied by 0.5FTE.
- Practice managers/administrative staff sex (male, female)
- Practice managers/administrative staff age group (<35 years; 35 to 50 years; >50 years)

Patient characteristics and pathology tests, medications prescribed, referrals and observations recorded at baseline (4th October 2021) for the closed cohort and at time of entry into the study for the open cohort, that will be extracted from the EMR include:

- Age (years)
- Sex (male, female, other)

- Hb (g/L)
- MCH (fL)
- MCV (pg)
- Ferritin (μg/L)
- Platelets (UI/ml)
- PSA (ng/ml)
- Free to total PSA (%)
- Recorded diagnosis of relevant cancer in the 5 years prior to baseline (yes/no)

Other information extracted from the EMR that occur during the trial period:

- Pregnancy
- Patient deceased

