4.4.5 Secondary outcomes analysis

Statistical methods described in the primary outcome will be used for the **binary secondary outcomes 1-5.**

Secondary outcome 6 will utilise a Poisson mixed effects model (or a Negative Binomial mixed effects model if overdispersion is detected), with fixed effects for study arm and the randomisation stratification factors (GP FTE and IRSD terciles), and random effect for general practice. The estimated intervention effect will be reported as differences in rate between the intervention and control arms and rate ratios with 95% confidence intervals and p-values.

Secondary outcome 7 will be analysed using a time to event analysis to compare the time to investigation for patients in the open cohort with an altered test results identified as at risk of an undiagnosed cancer between the study arms using a Cox proportional hazards model, adjusted for the randomisation stratification factors (GP FTE and IRSD terciles). Robust standard errors will be used to adjust for clustering effect by general practice. The proportional hazards assumption will be assessed following a two-step procedure: (1) calculate covariate specific tests and (2) plot the scaled and smoothed scaled Schoenfeld residuals obtained from the model.¹³ Kaplan-Meier survival curves will also be used to present time to event by study arm¹⁴, and the overall survival data will be summarised following a stratified proportional hazards model or a parametric model as appropriate.¹³ A sensitivity analysis using a competing risk analysis will be considered if patients at risk of undiagnosed cancer have died prior to an investigation/end of the trial follow-up period.

Estimates of the intervention effect will be reported as hazard ratios and 95% confidence intervals and p-value.

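### Cancer-risk secondary outcome 2 (oral supplement or iron infusion) is modelled without prior treatment, probably its strongest patient-level predictor; adding it is cheap

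*SAP*

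**What the plan says.** Section 4.2 of the cancer-risk SAP defines secondary outcome 2 as the proportion of anaemia-marker patients in the closed and open cohorts "that have subsequently been prescribed an oral supplement and/or have a record of an iron infusion in the 12-month trial period". The non-event rule is the mirror image: "The absence of any recorded prescription for an oral supplement or iron infusion will be considered equivalent of the patient not being prescribed" either. The definition sets when the record must fall. It does not require a new start and has no look-back.

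Under section 2.2, closed-cohort patients aged 50 to 80 enter if they are "without a recorded GI, unspecified or metastatic cancer in the last 5 years who have one marker of anaemia" within the stated window, which is "in the past 6 months or two consecutive markers of anaemia in the past 12 months". The exclusions are inactive or deceased patients and "Patients that are pregnant at baseline". Iron or other supplement use appears in neither list.

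Section 4.3 introduces its patient-level items as "Patient characteristics and pathology tests, medications prescribed, referrals and observations recorded at baseline" for the closed cohort, and at entry for the open cohort. The list that follows holds age, sex, laboratory values and cancer history, with no medication. Table 2 has none either.

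Section 4.4.5 states: "Statistical methods described in the primary outcome will be used for the" binary secondary outcomes 1 to 5. Besides study arm, the covariates in those models (section 4.4.4) are GP FTE and IRSD terciles. Sensitivity analysis 1 (section 4.5.1) adds QI participation, age, sex and cohort. The subgroups in section 4.5.7 are cohort, sex and age.

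**The concern.** A closed-cohort patient may have had the qualifying blood result up to 6 months before 4 October 2021, or up to 12 months before if there were two consecutive markers. Some may therefore have been started on treatment before the trial. A later repeat prescription for such a patient counts as an outcome event in either arm.

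Prior treatment is in effect the baseline value of the outcome, and so probably its strongest patient-level predictor. Leaving it out costs precision. It also leaves chance differences between practices in prior treatment unadjusted and, because the variable is not in the baseline table, unseen. There is a question of interpretation too: the overall effect mixes patients who could start treatment with patients who were already on it, and a reader cannot separate the two.

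**Working it through.** **No figure to reproduce.** The SAP gives no sample size, expected rate or prior-treatment share for outcome 2. All rates below are assumptions, used only to show scale. Clustering is ignored throughout.

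**1. Share of variance explained by prior treatment.** Let q be the share already treated, r the probability of a later record in those patients, and s the probability in untreated patients. Then the overall proportion is p = q·r + (1−q)·s, and the share explained is R² = q(1−q)(r−s)² / [p(1−p)]. Assume r = 0.70 and s = 0.175, so (r−s)² = 0.525² = 0.2756.

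- q = 0.10: p = 0.2275; R² = 0.0248 / 0.1757 = 0.14
- q = 0.25: p = 0.3063; R² = 0.0517 / 0.2125 = 0.24
- q = 0.40: p = 0.3850; R² = 0.0662 / 0.2368 = 0.28

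**2. Chance imbalance.** An arm difference d in prior treatment moves the unadjusted difference by about d·(r−s). If by chance 23% v 27% were already treated (d = 0.04), with s = 0.15 and r = 0.60 to 0.80, the shift is 0.04 × 0.45 = 1.8 points to 0.04 × 0.65 = 2.6 points. The split is invented for illustration.

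**3. Overall effect against the effect in untreated patients.** If r is the same in both arms, the overall risk difference is (1−q) times the difference in untreated patients. Assume new starts of 15% v 20% (difference 5.0 points, odds ratio 1.42) and r = 0.60 to 0.80. The adjusted columns are main-effect binomial models, with identity and logit links, fitted to the expected proportions with prior treatment as a covariate and independent observations.

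| q | Overall difference (points) | Overall odds ratio | Adjusted difference (points) | Adjusted odds ratio |
|---|---|---|---|---|
| 0.25 | 0.75 × 5.0 = 3.75 | 1.18–1.20 | 3.9–4.2 | 1.25–1.29 |
| 0.40 | 0.60 × 5.0 = 3.0 | 1.13–1.14 | 3.1–3.6 | 1.18–1.22 |

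At q = 0.10 the overall difference is 4.5 points and the odds ratio 1.28–1.30. In the table the adjusted estimates stay well below 5.0 points and 1.42: the covariate still averages over treated and untreated patients.

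**4. When the difference does not shrink.** Step 3 needs equal repeat rates in the two arms. Take 30% already treated, new starts of 20% v 30%, and repeats of 80% v 90%. The proportions are 0.3 × 0.8 + 0.7 × 0.2 = 0.38 and 0.3 × 0.9 + 0.7 × 0.3 = 0.48, and the difference is the full 10 points.

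**The case against.** The best defence is that the outcome does what its objective asks. Secondary objective 2 in section 1.3 concerns the proportion with a prescription or infusion recorded during follow-up, and section 4.2 presents the secondary outcomes as indicators of guideline-concordant care. A patient who stays on treatment meets that by design. This stands: a reader might infer that the definition contradicts the plan or is an error, and the documents do not support that.

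Nor do they support three other readings.

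- **The effect must be diluted.** Section 2.5 describes the module as identifying patients who may benefit from further follow-up and does not limit it to untreated patients. A flag could prompt renewal of a lapsed prescription, and step 4 shows that the difference then need not shrink.
- **The result is biased towards one arm.** Practices are randomised, so prior treatment is balanced in expectation. Chance imbalance is sampling error, which the robust standard errors are meant to reflect.
- **The CKD SAP adjusts all its prescribing outcomes at patient level.** Its primary outcome is also a prescribing outcome and has only the stratification factors (section 4.6.1). The fair comparison is with CKD secondary outcomes 1 and 2, covered by "For each outcome, an additional covariate will be fitted in the regression model" in section 4.6.2. That covariate is whether a recommendation to initiate the drug class would have been made, which is related to prior use but is not the same thing.

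What survives is narrower: an available, strongly prognostic variable is neither reported nor used.

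**Conclusion.** The point holds as an inexpensive improvement to one secondary outcome. Outcome 2 counts any later prescription or infusion, and prior treatment is not excluded, listed or adjusted for. The consequences are lost precision, unadjusted chance imbalance between practices and, only if repeat prescribing is unaffected by the module, an overall effect smaller than that in untreated patients by the factor (1−q).

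The scale is conditional. With 10–40% already treated, 70% repeat and 17.5% new-start rates, prior treatment would account for roughly 14–28% of the outcome variance before clustering. None of these rates is in the documents, and a lower prior-treatment share would make the gain smaller. A reader might also infer that the primary result is at risk, because the same events are one component of the primary composite in section 4.1. Nothing here shows that: the composite has many other components, and this check did not assess it.

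**What to change.** - **Derive** a yes/no variable for an oral supplement prescribed or an iron infusion recorded in the 12 months before entry. Entry is 4 October 2021 for the closed cohort and the index result date for the open cohort.
- **List** it in section 4.3 and Table 2, which also makes good the reference to medications in the section 4.3 introduction.
- **Add** it as a covariate to both outcome 2 models (logit and identity link) in section 4.4.5.
- **Keep** the full-cohort outcome as the main analysis, in line with the objective.
- **Report** outcome 2 also in patients with no prior treatment, as a supplementary analysis. Only this addresses dilution; the covariate serves precision and chance imbalance.

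The cost is one derived variable and a few sentences. The source looks available: section 2.5 of the CKD SAP bases baseline medication status on the entire prescribing history, and both SAPs draw on the Patron database. The supplementary report has a smaller denominator. The adjusted odds ratio becomes conditional on prior treatment and, as step 3 shows, need not equal the unadjusted one even with perfect balance, so the SAP should say which is reported.
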